## 1 Protocol Summary

|                         |  |
|-------------------------|--|
| SPONSOR                 | 
ADOREPS
 
Association pour le Développement et l'Organisation de la Recherche en
Pneumologie et sur le Sommeil
Service de Pneumologie et Réanimation Médicale
Groupe Hospitalier Pitié-Salpêtrière
[name]
[name]
  |
| TITLE                   | Emotional perception and production in Facial Palsy : Respiratory, Vocal and Facial markers.   |
| INVESTIGATEUR PRINCIPAL | [name]  |
| Numbers of centers      | Monocentric : Groupe Hospitalier Pitié-Salpêtrière   |
| Study Design            | Prospective study ;   |
| Introduction            | 
Respiratory function, phonation and facial expressivity are related to emotional reaction through neurophysiological process. Specific emotional respiratory, vocal and facial patterns had been described in literature. Respiratory cycles variation is modulated by stimulus arousal. Furthermore, inspiratory-to-expiratory time ratio in abdominal area is modulated by emotional valence. Inextricably linked to respiration, vocal production depends on emotional arousal and valence too.
 
According to embodied cognition, the effector pattern of an emotion initiates the corresponding subjective activation. Facial recognition is influenced by automatic mimicry and facial feedback. To our knowledge, most facial feedback studies included patients with diplegia but few studies dealt with emotional perception in Bell's palsy. Facial paralysis is a common pathology which concerns 20/100 000 inhabitants per year. Sudden and visible trauma, facial palsy affects voluntary and emotional motricity.
 
The aim of the present study is to understand production and perception of emotion in Bell's palsy with respiratory, vocal and facial markers. What impact lack of mimicry have on physiological emotional reaction in Bell's palsy? To this end, prospective monocentric study will be conducted with 60 patients with Bell's Palsy from grade II to grade VI of House & Brackmann's scale. During production and perception of vocal and facial expression, respiratory rate and thoraco-abdominal movements will be analyzed. We hypothesize that severity of facial deficit is negatively correlated with variation of respiratory cycles, lower segmental and suprasegmental changes during vocal expression, and lower facial perception (congruency and arousal).
 |

|                               |  |
|-------------------------------|--|
| OBJECTIVES             | 
Main Outcome
 
1) Effects of facial impairment on the respiratory rate.
 
Secondary Outcome
 
2) Effects of facial impairment on pitch variation (Hz) during emotional vocal production.
 
3) Effects of facial impairment on perception of emotional facial displays.
  |
| Endpoints              | 
1) Facial impairment assesed with Sunnybrook Facial Grading Scale. Respiratory rate is measured with chest and abdominal belt.
 
[Time Frame: 1hour]
 
2) Acoustic measures lead with Praat Analysis software. Variation pitch between first and last segment of the emotional sentence calculated.
 
[Time Frame: 1hour]
 
3) Emotional facial displays perception measured with a standardized emotional program in terms of congruency.
 
[Time Frame: 1hour]
 |
| Inclusion Criteria     | 
 
• Patients affiliated to the health care system
 
• Patients must have been diagnosed with unilateral peripheral facial palsy stage III to VI, according to House and Brackmann international classification.
 
• To be able to read, understand and sign a consent
 
• To be able to understand French spoken and written
 
  |
| Exclusion Criteria     | 
 
• Diplegia or facial graft
 
• Visual disorders, non corrected
 
• Respiratory or vocal disorders
 
• Psychiatric history
 
• Facial surgery
 
   |
| Number of participants | 60 participants.   |
| Statistical Analysis   | Mutlivariate analyses, regression analyses as well as Spearman correlations will be conducted. An ANOVA will be carried out with severity grade, facial paralyis side, sex of the patients.  |
| Study Duration         | Participation duration : 3hours
Study Duration : 20 month   |

## 2 Introduction

### 2.1 Title

Emotional perception and production in Facial Palsy : Respiratory, Vocal and Facial markers.

### 2.3 Study design

It is a prospective monocentric study.

## 3 Scientific Rationale

**Peripheral facial palsy :** facial palsy is a frequent pathology as far as it concerns 20/100 000 inhabitant a year [1]. deficits can remain in 29% of the cases : Peitersen lists 12% of mild sequellae, 13% of moderate sequellae and 4% of severe sequellae.

Visible and sudden trauma, facial impairment is multidimensional. Indeed, it concerns not only the voluntary facial motricity but also the spontaneous emotional facial motricity through the production of universal primary facial expressions [3]. Besides, the facial paralysis impacts patients' quality of life thus implying psychosocial difficulties. In acute or chronic phase, the main complaint of the patients deal with emotional expressiveness, especially happiness through a large smile. Literature highlights an increase of anxious and depressive symptoms in patients with facial palsy [5]. Inability to express a smile is involved in increased depressive symptoms [6]. Lack of facial feedback would also explain the decreasing feeling of well-being during smile production [7].

Respiratory, vocal and articulatory processing are modified by cognitive, autonomous and somatic change during emotional contagion. According to James-Lange theory [8], updated by embodied cognition [9], somatic experiences create emotions : to be conscious of physical changes and generated proprioceptive feedback give rise to emotions. On the other hand, six basic emotions could be distinguished in Ekman's paradigms. Each basic emotion implies specific autonomous, expressive and neuronal patterns : anger, disgust, fear, joy, sadness, surprise [10]. Two neurophysiological dimensions characterize emotion : arousal (activation level) and valence (pleasing aspect of a situation) [11].

### ***3.1 Emotions and Breathing***

Breathing is modulated by arousal of a stimulus [12]. During pictures displays, an intense activation increases the variability of respiratory cycles [13]. According to Boiten's review [14], increased respiratory rate would appear in high arousal emotions. Change in respiratory rate would result more from arousal effect than valence. Besides, there would be six different respiratory patterns. Inspiratory and expiratory time ratio increase in thoracic level and decrease in abdominal level during highly negative emotion. Opposite pattern is observed for positive emotion [15].

According to Glaus and al., (1983) [16] and Kotses et al. (1987), airflow resistance is correlated to increased facial muscle tension, measured by electromyography, which suggests an influence of facial muscles on the air resistance through a neuronal reflex. In chronic phase of facial palsy, it would be relevant to study respiratory capacity and facial hemispasm.

### ***3.2 Emotions and Vocal production***

Breathing and vocal production are indissociable ways to convey emotions. In a segmental framework, highly activation such as fear, anger or joy increases intensity and pitch whereas segment length decreases. On the contrary, sadness outputs decreased pitch and intensity and lengthening segment duration [18].

### ***3.3 Emotions and facial expressivity***

Emotional facial display perception implies an automatic neuronal activation in premotor cortex of the observers, the same as the one they would have conceived, if they were their own actors of the emotional facial expression observed [19]. Furthermore, emotion is processing by unconscious facial mimicry, which allow the observer to understand mental

state of others. Sensorimotor simulation is an other input of emotional percept construction [20].

Facial palsy affects non verbal communication by impairing emotional facial displays contagion [21]. Facial palsy implies cortical sensorimotor changes because of acute peripheral deafferentation [22]. To our knowledge, studies about facial mimicry and facial feedback in patients with facial palsy deal with diplegia [23-24]. Few studies explore emotional perception in unilateral peripheral facial palsy.

Multidimensional assessment of physiological activity is required to describe somatic states of basic emotion. We would like to study emotion encoding and decoding in patients with facial palsy by focusing on respiratory and vocal markers as well as facial expressivity and perception.

## 4 Objectives

### 4.1.1 Main Outcome

Effects of facial impairment on the respiratory rate.

### 4.1.2 Secondary Outcomes

- Effects of facial impairment on pitch variation (Hz) during emotional vocal production.
- Effects of facial impairment on perception of emotional facial displays.

## 5 Study Design

### 5.1 Study Duration

Participation duration : 3 hours

Study duration : 20 months

### 5.2 Définition de la population étudiée

Recruitment process will be carried out in the ENT department of Pitié-Salpêtrière Hospital.

### 5.2.1 Critères d'inclusion

- Patients affiliated to the health care system
- Patients must have been diagnosed with unilateral peripheral facial palsy stage III to VI, according to House and Brackmann international classification.
- To be able to read, understand and sign a consent
- To be able to understand French spoken and written

## 5.2.2 Critères de non-inclusion

- Diplegia or facial graft
- Visual disorders, non corrected
- Respiratory or vocal disorders
- Psychiatric history
- Facial surgery

## 5.3 *Methods*

[figure not shown]
### 5.3.1 Schedule of activities

The schedule of activities below shows the assessments that will be accomplished at each study visit. (X) means assessment usually conducted in facial palsy rehabilitation and (R) means assessment specific for the research.

|   | Facial Rehabilitation | Research |
|---|-----------------------|----------|
| Information and consent                       |                       | R        |
| Inclusion and Exclusion Criteria verification |                       | R        |
| History of health                             | X                     |          |
| Objective assessment                   |                       |          |
| Grading House & Brackman                      | X                     |          |
| MBLF Informatisée                             | X                     |          |
| Bilabial pression (dynamomètre)               | X                     |          |
| Photos and videos recording                   | X                     |          |
| Smile Scale                                   | X                     |          |
| Subjective questionnaires              |                       |          |
| STAI questionnaire                            |                       | R        |
| PANAS scale                                   |                       | R        |
| Voice Handicap Index                          |                       | R        |
| Synkinesis Assessment Questionnaire           | X                     |          |
| Respiratory assesments                 |                       |          |
| Chest and abdominal belt                      |                       | R        |
| Spirometer                                    |                       | R        |
| Vocal assesment                        |                       |          |
| Acoustic measures                             |                       | R        |
| EVALAD reading                                |                       | R        |
| MEC tests                                     |                       | R        |

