### 5.3.2 Collecting Data

Figure 1 : Collecting Data

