### 5.3.3 Endpoints

#### 5.3.3.1 *Main outcome*

1) Facial impairment assessed with Sunnybrook Facial Grading Scale. Respiratory rate is measured with chest and abdominal belt.

[Time Frame: 1hour]

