#### 5.3.3.2 *Secondary outcomes*

2) Acoustic measures lead with Praat Analysis software. Variation pitch between first and last segment of the emotional sentence calculated.

[Time Frame: 1hour]

3) Emotional facial displays perception measured with a standardized emotional program in terms of congruency.

[Time Frame: 1hour]

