#### 5.3.4.2 *Analysis of endpoints*

Respiratory data are collected with the software Labchart whereas acoustic analyses are conducted with Praat Software ( Boersma & Weenik, 1996). Statistical analyses will be made with Excel Spreadsheet and JMP.10 software.

In order to analyse endpoints, multivariated analyses, regression analyses will be conducted. Spearman and Pearson correlation will be carried out in order to determine potential emotional markers. ANOVA analyses would be made to show any differences among patients according to severity of their palsy, facial palsy side, sex or questionnaire score.

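### Does the schedule table's silence on the Sunnybrook scale and the facial-emotion program leave two endpoints without their measurements?

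*Combined protocol and SAP*

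**What the plan says.** Section 5.3.1 presents its table as the list of what is done: "The schedule of activities below shows the assessments that will be accomplished at each study visit". The only row that grades the palsy as a whole is "Grading House & Brackman". The other objective rows are the MBLF, bilabial pressure, photographs and videos, and the Smile Scale. The research rows cover questionnaires, the belts, spirometry, acoustic measures, EVALAD reading and the MEC tests, the last under the vocal heading.

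The endpoints name other instruments. For the main outcome, section 5.3.3.1 has "Facial impairment assessed with Sunnybrook Facial Grading Scale", with respiratory rate taken from the belts. For the third endpoint, section 5.3.3.2 has "Emotional facial displays perception measured with a standardized emotional program in terms of congruency".

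House-Brackmann also sets eligibility, at "unilateral peripheral facial palsy stage III to VI" (5.2.1). On analysis, the summary says "An ANOVA will be carried out with severity grade", and section 5.3.4.2 plans an ANOVA for "differences among patients according to severity of their palsy". Neither sentence names the scale. Section 5.3.2, directly after the table, has as its content only "Figure 1 : Collecting Data", and that figure is not visible in the text available for review.

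**The concern.** A schedule table is often the page that staff work from. Read alone, this one would lead them to grade the palsy by House-Brackmann only and to omit the perception program. The main outcome would then lack its stated exposure, and the third endpoint its outcome. A severity score missed on the day of the belt recording may not be recoverable for that time point.

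The second worry concerns analysis. If both scales are collected and the analysis text says only severity, an analyst could try each and report the more favourable one. The word grade suggests House-Brackmann, while the endpoint section says Sunnybrook. The difference matters because an ordinal grade fits an ANOVA factor, whereas a score fits regression or correlation.

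There is also a smaller mismatch. The summary's hypothesis on facial perception covers both congruency and arousal, but the third endpoint keeps congruency only.

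**Working it through.** **Instruments against the table.** The three endpoints need four instruments.

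| Instrument | Needed for | Row in 5.3.1 |
|---|---|---|
| Sunnybrook scale | Main outcome (exposure) | No |
| Chest and abdominal belt | Main outcome (response) | Yes |
| Acoustic measures | Second endpoint | Yes |
| Facial-emotion program | Third endpoint | No |

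So 2 of 4 have no row, and they affect 2 of the 3 endpoints.

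**Is the exposure of the main question named?** Objective 1 is the effect of facial impairment on respiratory rate (4.1.1). Section 5.3.3.1 and the summary both say that facial impairment is measured with Sunnybrook. The term is the same in both places, so the exposure is named. The unnamed severity wording occurs only in the ANOVA sentences, beside side and sex. Section 5.3.4.2 lists regression and correlation separately from that ANOVA.

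**Is there evidence that the measurements would be skipped?** The content of section 5.3.2 is a figure that cannot be read here. References 25 to 34 in the bibliography are mostly instruments and software, with Sunnybrook as number 29, and none is cited by number in the readable text. That is consistent with citation in a figure but does not prove it. No comparable reference was found for the facial-emotion program, so this inference is weaker there.

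**What would the choice of scale cost?** The plan gives no effect size, significance level or sample-size calculation, so it has no figure to reproduce. The following is illustrative: n = 60, bivariate normal data, two-sided 5%, assumed correlation r, and House-Brackmann as four equal quarters of the same underlying severity. Simulated power:

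| r | Pearson, score | Spearman, score | Spearman, four grades | ANOVA, 3 df |
|---|---|---|---|---|
| 0.25 | 0.49 | 0.45 | 0.41 | 0.28 |
| 0.355 | 0.80 | 0.75 | 0.71 | 0.56 |
| 0.45 | 0.96 | 0.94 | 0.91 | 0.82 |

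At r = 0.355 the drop from Pearson to ANOVA is 0.80 − 0.56 = 0.24. It splits as follows:
- Pearson to Spearman: 0.80 − 0.75 = 0.05
- score to grades: 0.75 − 0.71 = 0.04
- rank correlation to 3-df ANOVA: 0.71 − 0.56 = 0.15

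The scale itself therefore accounts for 4 of 24 points. Over r from 0.25 to 0.45, with equal or unequal grades, the scale costs about 3 to 6 points, and the whole change of scale and test costs 14 to 26.

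**False positives from choosing afterwards** (same set-up with no effect, correlation between scales assumed from 1.0 down to 0.7):
- Spearman on whichever scale gives the smaller p-value: about 6% to 9%.
- Free choice among Pearson or Spearman on Sunnybrook and Spearman or ANOVA on House-Brackmann: about 11% to 13%.
- Choice of test within one scale only: about 8% on House-Brackmann and about 6.5% on Sunnybrook.

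The last line shows that part of the 11% to 13% would remain after a scale had been named.

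**The case for a change.** The strongest case for a change is that the table is not a short list. It itemises lesser measures such as bilabial pressure and spirometry, so leaving out the measure behind the main outcome is conspicuous. All three objectives are framed as effects of facial impairment, so the impairment score bears on every endpoint. Even if the figure lists both instruments, the table would disagree with it, and the ANOVA sentences would still name no scale. Correcting this would cost two rows and a sentence.

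The observation stands: the table and the endpoints do not agree, and the ANOVA factor is unnamed. The harm is less secure. For Sunnybrook the two feared outcomes exclude each other. If it is not collected, there is no choice of scale to exploit; if it is collected, the missing row is clerical. That staff at this single centre would follow the table and ignore the endpoint section is conjecture. Low cost does not make the matter consequential, since the edits would only write down what the endpoint sections already require. Making a continuous Sunnybrook score primary, with House-Brackmann as a sensitivity analysis, would be a reasonable preference, but the documents do not demand it. On arousal, a hypothesis may be broader than the endpoint chosen to test it.

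**Conclusion.** No change to the plan follows. Read as a whole, the protocol requires both measurements. It names Sunnybrook as the measure of facial impairment for the main outcome, and it lists the regression and correlation analyses in which a score would be used. The missing rows are a clerical slip, and an analyst working from section 5.3.3 would resolve the unnamed ANOVA factor sensibly. Making the table match the endpoints whenever the document is next edited would be housekeeping.

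In size, two of four endpoint instruments are missing from one table. The effect attributable to the scale is about 3 to 6 points of power, or a false-positive rate of about 6% to 9% instead of 5% if the scale were picked after the fact. These figures rest on an assumed effect size, significance level, grade distribution and correlation between scales, in a study that calls itself exploratory (5.3.4.1). The larger figures mainly reflect the open choice of test, which is a separate matter.

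The conclusion is limited by the unread figure in 5.3.2. The readable text shows a disagreement between the table and the endpoints; it does not show that either measurement goes uncollected.

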### 5.3.2 Collecting Data

Figure 1 : Collecting Data

### 5.3.3 Endpoints

#### 5.3.3.1 *Main outcome*

1) Facial impairment assessed with Sunnybrook Facial Grading Scale. Respiratory rate is measured with chest and abdominal belt.

[Time Frame: 1hour]

#### 5.3.3.2 *Secondary outcomes*

2) Acoustic measures lead with Praat Analysis software. Variation pitch between first and last segment of the emotional sentence calculated.

[Time Frame: 1hour]

3) Emotional facial displays perception measured with a standardized emotional program in terms of congruency.

[Time Frame: 1hour]

### 5.3.4 Statistical consideration

#### 5.3.4.1 *Sample size determination*

There is lack of precise data in the literature on this theme, it is impossible to make a calculation of sample size. With the aim of an exploratory study, we would like to study at least 60 patients in order to be able to conduct multivariated analysis.

#### 5.3.4.2 *Analysis of endpoints*

Respiratory data are collected with the software Labchart whereas acoustic analyses are conducted with Praat Software ( Boersma & Weenik, 1996). Statistical analyses will be made with Excel Spreadsheet and JMP.10 software.

In order to analyse endpoints, multivariated analyses, regression analyses will be conducted. Spearman and Pearson correlation will be carried out in order to determine potential emotional markers. ANOVA analyses would be made to show any differences among patients according to severity of their palsy, facial palsy side, sex or questionnaire score.

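### The ANOVA on questionnaire score implies groups that the plan never defines, and its two descriptions differ; each score is better fitted as a continuous term beside severity, side and sex

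*Combined protocol and SAP*

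**What the plan says.** Section 5.3.4.2 (Analysis of endpoints) states: "ANOVA analyses would be made to show any differences among patients according to severity of their palsy, facial palsy side, sex or questionnaire score". The Statistical Analysis row of section 1 (Protocol Summary) states: "An ANOVA will be carried out with severity grade, facial paralyis side, sex of the patients". The first includes questionnaire score and the second does not. Neither gives a model, a grouping or a cut-point.

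The schedule in section 5.3.1 lists four subjective questionnaires: the "STAI questionnaire", the PANAS scale, the "Voice Handicap Index" and the "Synkinesis Assessment Questionnaire".

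Section 5.3.4.2 also says: "In order to analyse endpoints, multivariated analyses, regression analyses will be conducted", and "Spearman and Pearson correlation will be carried out in order to determine potential emotional markers". No outcome, predictor or covariate is named for any of these. Section 5.3.4.1 gives no sample size calculation. It calls the study exploratory and says: "we would like to study at least 60 patients in order to be able to conduct multivariated analysis".

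**The concern.** ANOVA compares group means. Severity grade, side and sex come as categories, but a questionnaire score does not. To compare patients by score in an ANOVA, someone must decide how many groups to form and where to cut. The plan fixes neither, so the choice would be open when the data are in hand, for four questionnaires and three outcomes. Grouping also costs power, which is scarce with 60 patients.

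A second and separate matter is whether sex is in the model when a score is tested. If women and men differ both in a score and in an outcome, a model without sex can credit the score with a difference that belongs to sex. The text does not say which model is meant.

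**Working it through.** **Inputs.** N = 60 is from section 5.3.4.1. The documents give no alpha, power, effect size or SD, so there is no figure of the plan's own to reproduce. Assumed here: two-sided alpha of 5%, a normally distributed score, and a range of correlations r between score and outcome.

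**1. Information kept by grouping.** For a standard normal score cut into groups with proportions p_k and within-group means m_k, the share of variance kept is the sum of p_k × m_k². For a median split this is 2/π = 0.637, so 36% is lost and 60 patients count as 60 × 0.637 = 38.

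| Grouping | Information lost |
|---|---|
| Quintiles | 10% |
| Quartiles | 14% |
| Tertiles | 21% |
| Median split | 36% |
| 30/70 split | 42% |
| 25/75 split | 46% |
| 20/80 split | 51% |

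**2. Power.** With k groups keeping a share c, R² = r² × c, f² = R²/(1 − R²), and the test is a noncentral F with k − 1 and N − k degrees of freedom and noncentrality N × f². The continuous term has c = 1 and 1 and 58 degrees of freedom.

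At r = 0.30 the noncentralities are:
- continuous: 60 × 0.09/0.91 = 5.93
- median split: R² = 0.09 × 0.637 = 0.0573, giving 60 × 0.0573/0.9427 = 3.65
- tertiles: R² = 0.09 × 0.793 = 0.0714, giving 4.61
- quartiles: R² = 0.09 × 0.861 = 0.0775, giving 5.04

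| r | Continuous | Median split | Tertiles | Quartiles |
|---|---|---|---|---|
| 0.20 | 34% | 23% | 21% | 19% |
| 0.30 | 67% | 47% | 45% | 42% |
| 0.40 | 91% | 73% | 73% | 71% |

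At r = 0.30 the loss is 20 to 25 percentage points. Finer groups keep more information but spend more degrees of freedom, so they do not win the power back. These are single-predictor calculations; covariates would alter both sides of the comparison.

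**3. Leaving sex out.** 20,000 simulated trials per scenario, with 60 patients, 30 of each sex (assumed) and no true effect of the score on the outcome. Sex shifts the score and the outcome by the stated numbers of SD. The table gives the rejection rate for the score at a nominal 5%.

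| Shift in score / outcome (SD) | Median split, no sex | Continuous, no sex | Median split, sex fitted | Continuous, sex fitted |
|---|---|---|---|---|
| 0 / 0.5 | 4.9% | 4.6% | 4.9% | 4.8% |
| 0.3 / 0.3 | 4.8% | 5.0% | 4.7% | 4.8% |
| 0.5 / 0.5 | 6.5% | 7.2% | 4.8% | 4.7% |
| 0.5 / 0.8 | 8.6% | 11.0% | 4.7% | 4.9% |
| 0.5 / 1.0 | 10.1% | 13.0% | 5.0% | 5.1% |
| 0.8 / 0.8 | 14.3% | 18.3% | 5.1% | 4.8% |

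The inflation comes from omitting sex. Grouping does not cause it: wherever there is inflation, the ungrouped score shows slightly more of it. With sex in the model the rate is about 5% throughout.

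**The case against.** The plan is loosely worded rather than visibly wrong, and several stronger readings that a reader might infer go beyond it.

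- *Scores will be cut at points chosen from the data.* No grouping is stated. That an ANOVA on a score needs groups is a reasonable inference, but it remains an inference.
- *Each factor is tested alone.* This rests on the word *or* in a list. The Protocol Summary describes a single ANOVA with grade, side and sex, regressions are planned, and the sample size is justified by multivariate analysis. All of this points towards joint fitting, although none of it mentions the scores.
- *A third of the information is thrown away.* That figure belongs to a median split of a normal score. Other groupings lose about 10% to 51%, and the planned correlations could use the scores ungrouped.
- *A sex difference will pass as an anxiety or mood effect.* This needs sex to be related to both score and outcome, and the documents give no figure for either. The pitch outcome is a change between the first and last segments of a sentence, so its being in Hz does not by itself show a sex difference.

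These objections stand against the stronger readings. They do not remove the gap. The ANOVA sentence is the only one that says how questionnaire scores are used. The regressions and correlations name no variables, so they cannot be relied on to treat the scores differently.

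It is also fair that the stakes are limited. The study is exploratory, and questionnaire scores appear in no objective or endpoint.

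**Conclusion.** The point holds as a cheap improvement to supporting analyses. The method named for questionnaire scores implies groups that the plan leaves undefined, the two descriptions of the ANOVA differ on whether scores are included, and neither says whether a score is fitted jointly with sex.

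If the scores are grouped, the expected cost is 20 to 25 points of power at r = 0.30 with two to four groups, given a normal score and a two-sided 5% test. The risk from omitting sex is conditional and cannot be sized from the documents. Over the sex differences tried, it runs from none to a clear excess of false positives, and fitting sex removes it. No conclusion follows for the main question of facial impairment and respiratory rate.

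**What to change.** In section 5.3.4.2, take questionnaire score out of the ANOVA sentence. State instead that each outcome is analysed by one regression with severity, side and sex, and that each questionnaire score is added to it in turn as a continuous term with one degree of freedom and no cut-points. Use the same wording in the Statistical Analysis row of the Protocol Summary. Group means may be shown for description, without a test.

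The cost is one sentence in each of two places. No further data are needed, and regression in JMP is already planned. If joint fitting was intended all along, the edit simply records it. The drawback is that a continuous term assumes a roughly linear relation between score and outcome, which a plot can check.
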